#### Arm A-1: Standard Low Glucose Parenteral Nutrition using Eurotubes®

Patients randomized to treatment Arm A-1 will receive PN reduced in glucose in Eurotubes® (Eurozyto).

The following displays a guidance for the PN composition administered in Arm A-1. The amounts listed are understood as daily dose. Underlying medical conditions, intolerance etc. must always be considered per individual patient.

#### Macronutrients:

For the macronutrients, body weight is understood as the ideal body weight for the patient according to a BMI of 19 - 24 for women and 20 - 25 for men.

Glucose: 1.0 - < 2.0 g per kg body weight

Amino acids: 1.2 - 1.5 g per kg body weight

Lipids: 0.5 - 2.0 g per kg body weight

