#### Arm B: Standard Parenteral Nutrition using 2/3-chamber bags.

Patients randomized to Arm B will receive PN according to the routine used by the participating site.

Patients in Arm A will be stratified again by the same criteria as listed above and randomized in a 1:1 ratio to Arm A-1 or Arm A-2:

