# **Arm A-2**: Standard Parenteral Nutrition using Eurotubes®.

Patients randomized to Arm A and in a second randomization to treatment Arm A-2 will receive standard PN in Eurotubes®.

Patients will be recruited during regular consultation visits.

An overview of the study scheme is given in Figure 1.

-CONFIDENTIAL- Page 14 of 33

[figure not shown]

Figure 1: Study Scheme.

-CONFIDENTIAL-

At screening and at all regular visits during the HPN treatment period (one visit per four-week interval after randomization for a maximum of 12 months) the ECOG performance status and body weight will be determined. Additionally, physical examinations and laboratory assessments including CRP, albumin and total protein levels will be performed. Laboratory assessments do not need to be repeated at screening if laboratory assessments were done prior to screening within clinical routine and results are not older than 2 weeks. The type of catheter used for parenteral nutrition will be documented (Port-a-Cath, Hickmann/Broviac catheter etc).

The HPN therapy and any modifications and adjustments to this plan during the course of HPN treatment will be recorded from visit 1 onwards.

Anti-cancer treatment at the time of screening and any changes during the course of the HPN treatment period (e.g. type of treatment) will be documented.

Monitoring of Adverse Events and medical device deficiencies will be performed at every visit. AEs will be graded according to the National Cancer Institute's Common Terminology Criteria for Adverse Events (NCI CTCAE) version 5.0.

During the study the patient will maintain a study diary to document details of the administration of the HPN. A QoL questionnaire will be completed during regular study visits until EOT.

After completion of study treatment, patients will enter the follow-up period. During this period, they will be followed approximately every 3 months for survival which can be done by phone.

-CONFIDENTIAL- Page 16 of 33

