#### 5.1.2 Secondary Objectives

#### Secondary Objectives

- To compare the incidence of catheter related infections (CRI) between treatment Arms A and B in the per protocol population.
- To compare the efficacy of PN in terms of body weight, C-reactive protein (CRP) and albumin levels, and overall survival (OS)
- To compare the Quality of life (QoL) by use of the MODIFIED HPN-PROQ questionnaire
- To determine the frequency of PN-related visits by the nursing service
- To compare the safety in terms of the incidence of other catheter related complications, severe, common toxicity criteria (CTC) grade 3-5 infections, and PN-related Adverse Events (AEs)

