#### Secondary Endpoints

All secondary analyses, excluding safety endpoints analyses, which will be based on the safety population, and the CRI, which will be based on the per protocol population, will be based on the ITT population. Sensitivity analysis of the primary endpoint and other important endpoints will be performed in the per protocol population, also. The parameters will be evaluated in an explorative manner, providing means, medians, ranges, standard deviations and/or confidence intervals. Rates will be compared using fisher's exact test and continuous variables using t-test. For the time-to-event variable OS, the Kaplan-Meier method will be used, and treatment groups will be compared using a log rank test. All resulting p-values for secondary endpoints will be considered descriptive and will be presented explicitly without referring to hypotheses or a significance level. Usually, no p-value adjustment for multiple-testing will be performed. Thus, the p-values will reflect the comparison-wise error and not the experiment-wise error. All p-values will be two-sided if not stated otherwise. The statistical methods described in this section are suited for the data and distributions usually expected in this type of trials. The suitability will be checked and if necessary, the statistical method will be modified accordingly, with critical discussion of the original and modified results.

Further details of the planned procedures and specific analyses will be defined in the statistical analysis plan, latest prior to locking the database.

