### 8 Therapy scheme

The S3-Guideline of the German Society for Nutritional Medicine for Clinical Nutrition in Oncology should be used as guidance when setting-up the PN therapy plan [S3-Guideline of the German Society for Nutritional Medicine (DGEM) in Cooperation with the DGHO, the ASORS and the AKE, Clinical Nutrition in Oncology].

The following must always be considered before determining the patient's therapy scheme:

• For all treatment arms the composition of the nutrients can differ from the tables below due to site-specific routine or investigator's/medical decision.

-CONFIDENTIAL- Page 23 of 33

\*There are no data that indicate special gender distribution. Therefore, patients will be enrolled in the study gender-independently.

- The frequency of PN is not pre-determined for any treatment arm and can change during the course of the study based on the evolving nutritional status of the patient.
- The recommended infusion duration is 12-14 hours. However, the duration can differ and the maximum infusion speed per macronutrient should always be considered.
- If the run-in phase was not conducted at the inpatient facility, then a low energy nutrition should be considered for the start of HPN to avoid a refeeding syndrome.
- For Arm A-1 and Arm A-2 some modifications to the initially considered therapy plan
  might become necessary based on to the randomization results. These modifications
  should only be done if medically acceptable.

Note: Any existent clinical contraindications must always be of overriding importance compared to the randomization results and therapy as randomized should only be administered if medically acceptable.

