#### TOTAL:

Total Volume: 30 - 40 ml per kg body weight

Total Calories: 25 - 30 kcal per kg body weight

guidance for calculating calories:

1 g glucose ~ 4 kcal

1 g amino acids ~ 4 kcal

1 g lipids ~ 10 kcal

The investigator should specify the PN composition according to the site-specific routine in consultation with a nutritional expert, if routinely involved in the PN at this site, considering the guidance above. At the investigator's discretion he/she can also consult the Care Management/Supply Management of LIGETIS for advice and fine-tuning the PN composition.

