#### Arm B: Standard Parenteral Nutrition using 2/3-chamber bags

-CONFIDENTIAL- Page 26 of 33

Patients randomized to Arm B will receive standard PN using 2/3-chamber bags (various manufactures) according to the routine used by the participating site.

The following displays a guidance for the PN composition administered in Arm B. The amounts listed are understood as daily dose. Underlying medical conditions, intolerance etc. must always be considered per individual patient.

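### Half of Arm A is assigned a lower-glucose formula, so the secondary A versus B comparison of weight, CRP, albumin and OS mixes bag type with formula; A-2 versus B should be reported beside it

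*Combined protocol and SAP*

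**What the plan says.** Section 4 randomises patients 2:1 to Arm A or Arm B. Arm A patients are then "randomized in a 1:1 ratio to Arm A-1 or Arm A-2".

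Section 8 gives the composition by arm. For A-1 it is "Glucose: 1.0 - < 2.0 g per kg body weight"; for A-2 and for B it is 2.0 to 4.0 g/kg. Amino acids (1.2 to 1.5 g/kg) and lipids (0.5 to 2.0 g/kg) have the same printed ranges in all three arms, and so does the energy target: "Total Calories: 25 - 30 kcal per kg body weight". Section 3.1 names more fat as the consequence of less glucose and lists the benefit of this as an open question.

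These figures are not binding. The opening of Section 8 says that in all arms "the composition of the nutrients can differ from the tables below due to site-specific routine" or for medical reasons, and Arm B is given "according to the routine used by the participating site".

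Section 5.1.2 has two lists of secondary objectives. In the general list, the infection bullet names Arms A and B. The efficacy bullet names no arms: "To compare the efficacy of PN in terms of body weight, C-reactive protein (CRP) and albumin levels, and overall survival (OS". The second list is headed as A-1 versus A-2. Section 6.3.2 plans t-tests, Fisher's exact test and a log-rank test, with p-values presented "without referring to hypotheses or a significance level". Sections 5.1.2 and 6.3.2 do not state an A-2 versus B comparison.

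**The concern.** Section 2 defines standard PN by its composition. Sections 4 and 6.3.2 then label the whole of Arm A as standard PN in Eurotubes. A reader of the results would take A versus B to mean the same formula in a different bag. By randomisation, half of Arm A is assigned a different formula.

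Section 3.5 gives the missing evidence on Eurotubes against traditional bags as the reason for the trial. Weight, CRP, albumin and OS are outcomes on which formula could plausibly act. A formula effect could be read as an effect of the bag, or could hide one. The planned A-1 versus A-2 comparison estimates the formula effect, but the plan does not say that it will be used when A versus B is interpreted.

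**Working it through.** **Inputs.** Allocation 2:1, then 1:1 (Section 4). Sample size 128 + 64 = 192, and 216 with about 10% dropout (Section 6.1). Composition ranges and energy factors of 4, 4 and 10 kcal per g of glucose, amino acids and lipid (Section 8). PN planned on at least 3 days a week (Section 7.1). All effects on outcome below are assumptions; the documents give none.

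**1. The plan's sample size.** The Walters approximation for Fisher's exact test (5% versus 20%, two-sided 0.05, 2:1) gives 79.8% power with 126 + 63 and 80.5% with 128 + 64, so 192 is reproduced. For dropout, 192/0.9 = 213.3, so 214; the next multiple of 3 is 216. That is 144 in Arm A (72 + 72) and 72 in Arm B. The figure matters here only for the arm sizes.

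**2. What A versus B estimates.** With a 1:1 split, the Arm A mean is 0.5(A-1) + 0.5(A-2). Hence

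A − B = (A-2 − B) + 0.5 × (A-1 − A-2),

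that is, the difference under the same printed guidance plus half of the formula effect.

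**3. Glucose separation if guidance is followed.** The mid-range is 1.5 g/kg in A-1 and 3.0 in A-2 and B. Arm A averages (1.5 + 3.0)/2 = 2.25. The gap to B is 3.0 − 2.25 = 0.75 g/kg on PN days, and 0.75/3.0 = 25%. At 3 PN days a week it is 0.75 × 3/7 = 0.32 g/kg per calendar day.

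**4. Fat, if the energy target is also met.** At mid-range glucose with equal energy and amino acids, A-1 replaces 4 × 1.5 = 6 kcal/kg by 6/10 = 0.6 g/kg more lipid than B. At the edges of the guidance, A-1 needs more than (25 − 4 × 2.0 − 4 × 1.5)/10 = 1.1 g/kg lipid. A-2 and B can reach the target with 0.5 g/kg: 4 × 4.0 + 4 × 1.5 + 10 × 0.5 = 27 kcal/kg. These limits are conditional on the guidance and do not bind.

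**5. Effect on the A versus B estimate, for assumed formula effects.**
- Means: 0.2, 0.3 or 0.5 SD between A-1 and A-2 gives 0.10, 0.15 or 0.25 SD in A versus B.
- OS: hazard ratios of 0.9, 0.8 or 0.7 between A-1 and A-2 would appear as about exp(0.5 × ln HR) = 0.95, 0.89 or 0.84. This is an approximation.

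**6. Precision.** The standard error in SD units is √(1/n₁ + 1/n₂); the half-width is 1.96 times that.

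| Contrast | n | SE | 95% half-width |
|---|---|---|---|
| A versus B, all 216 | 144, 72 | 0.144 | 0.283 |
| A-2 versus B, all 216 | 72, 72 | 0.167 | 0.327 |
| A versus B, 192 | 128, 64 | 0.153 | 0.300 |
| A-2 versus B, 192 | 64, 64 | 0.177 | 0.346 |

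The ratio of standard errors is 1.155 in both cases.

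**7. Can A-2 versus B be derived from the planned contrasts?** Rearranging step 2, A-2 − B = (A − B) − 0.5 × (A-1 − A-2). With equal arm sizes and SDs the two planned contrasts are uncorrelated, so the standard error is √(0.144² + 0.25 × 0.167²) = 0.167, as in the table. This is exact for mean differences with equal A-1 and A-2 numbers and approximate for log hazard ratios.

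**The case against.** The strongest reply is step 7: the two planned comparisons already contain the missing contrast, and Section 6.3.2 promises means and standard deviations. This largely stands. What is missing is a commitment to report A-2 versus B and to use it in reading the bag effect. Without it, the choice can be made after the data are seen, and readers must do the subtraction themselves.

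The pooled A versus B comparison is a valid randomised comparison of Eurotubes as used in this trial. That stands too, and it should be kept. The A versus B reading of the efficacy bullet is inferred from its neighbours. Sections 6.3 and 6.3.2 defer details to an SAP that could still add A-2 versus B.

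A reader might infer more than the documents support:
- *That A-1 patients are underfed.* Holding lipid at 1.25 and amino acids at 1.35 g/kg with mid-range glucose gives A-1 6 + 5.4 + 12.5 = 23.9 kcal/kg, below target. But Section 3.1 names more fat as the consequence of less glucose, and A-1 has the same energy target as the other arms. This scenario departs from the plan.
- *That the lipid limits in step 4 are fixed.* Section 8 calls the A-1 and B lists guidance and allows departures in every arm.
- *That the protocol predicts a survival effect.* Section 3.6 speaks of tumour growth, not OS, and Section 3.2 says that the clinical data are too few for a conclusion.
- *That A-2 versus B isolates the bag.* Arm B follows site routine, and Section 8 foresees plan changes after randomisation in A-1 and A-2.

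**Conclusion.** The point holds as a matter of interpretation. For weight, CRP, albumin and OS, A versus B carries half of any formula effect, and the contrast with matching printed guidance is not planned. If guidance is followed, mid-range glucose on PN days is 25% lower in Arm A than in Arm B; actual separation may be smaller. The size of any effect on outcome is unknown. Every assumed shift of a mean in step 5 is below the A versus B half-width of about 0.28 SD, which itself assumes data from all 216 patients.

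It would be wrong to infer that the primary result or the type I error is at risk. The primary endpoint is who administers the PN, and the documents give no route by which glucose content would change that. Secondary p-values are descriptive. The change is worth making because it is cheap and bears on the bag question that the trial was set up to answer.

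**What to change.** Keep A versus B. In Sections 5.1.2 and 6.3.2, and in the SAP, pre-specify A-2 versus B (72 versus 72 planned) for the four endpoints. Suggested text:

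> For weight, CRP, albumin and OS, Arm A-2 versus Arm B is reported beside Arm A versus Arm B and is used to interpret the effect of bag type. For these endpoints Arm A is described as 'Eurotubes, half with low-glucose formula'. Arm A-2 versus Arm B removes only the randomised glucose difference, because Arm B follows site routine and plans in Arms A-1 and A-2 may be modified after randomisation.

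Also tabulate glucose, lipid and kcal per kg by arm, so that readers see the separation actually reached. Section 4 already provides the source: "The HPN therapy and any modifications and adjustments to this plan during the course of HPN treatment will be recorded from visit 1 onwards". This assumes that the record gives nutrient amounts, which the documents do not confirm.

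The cost is one descriptive contrast and one table. Treatment, visits, sample size and the primary test do not change. The added contrast is less precise: a standard error of 0.167 against 0.144 SD, so a confidence interval about 15% wider than for A versus B.

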#### Micronutrients:

Independent of the ideal body weight, should be added taken the actual serum levels into account.

Sodium: 60 - 150 mmolPotassium: 40 - 100 mmol

-CONFIDENTIAL- Page 24 of 33

Magnesium: 4 - 12 mmol

Calcium: 2.5 - 7.5 mmol

Phosphate: 10 - 30 mmol

#### **Trace Elements and Vitamins:**

Trace Elements and Vitamins are added according to the standard dietary reference intake.

#### Water:

The amount of water depends on the oral intake of water, volume tolerance and kidney function. As general guidance 30 - 40 ml per kg body weight should be considered.

#### TOTAL:

Total Volume: 30 - 40 ml per kg body weight

Total Calories: 25 - 30 kcal per kg body weight

guidance for calculating calories:

1 g glucose ~ 4 kcal

1 g amino acids ~ 4 kcal

1 g lipids ~ 10 kcal

The investigator should specify the PN composition according to the site-specific routine in consultation with a nutritional expert, if routinely involved in the PN at this site, considering the guidance above. At the investigator's discretion he/she can also consult the Care Management/Supply Management of LIGETIS for advice and fine-tuning the PN composition.

#### Arm A-2: Standard Parenteral Nutrition using Eurotubes®

Patients randomized to treatment Arm A-2 will receive standard PN in Eurotubes® (Eurozyto).

The following displays the specifications for the PN composition administered in Arm A-2. The amounts listed are understood as daily dose. Underlying medical conditions, intolerance etc. must always be considered per individual patient.

#### Macronutrients:

For the macronutrients, body weight is understood as the ideal body weight for the patient according to a BMI of 19 - 24 for women and 20 - 25 for men.

Glucose:  $\geq 2.0 - 4.0$  g per kg body weight

-CONFIDENTIAL- Page 25 of 33

Amino acids: 1.2 - 1.5 g per kg body weight

Lipids: 0.5 - 2.0 g per kg body weight

#### Micronutrients:

Independent of the ideal body weight, should be added taken the actual serum levels into account.

Sodium: 60 - 150 mmolPotassium: 40 - 100 mmolMagnesium: 4 - 12 mmolCalcium: 2.5 - 7.5 mmolPhosphate: 10 - 30 mmol

#### Trace Elements and Vitamins:

Trace Elements and Vitamins are added according to the standard dietary reference intake.

#### Water:

The amount of water depends on the oral intake of water, volume tolerance and kidney function. As general guidance 30 - 40 ml per kg body weight should be considered.

#### TOTAL:

Total Volume: 30 - 40 ml per kg body weight Total Calories: 25 - 30 kcal per kg body weight

guidance for calculating calories:

1 g glucose ~ 4 kcal

1 g amino acids ~ 4 kcal

1 g lipids ~ 10 kcal

The investigator should specify the PN composition according to the site-specific routine in consultation with a nutritional expert, if routinely involved in the PN at this site, considering the guidance above. At the investigator's discretion he/she can also consult the Care Management/Supply Management of LIGETIS for advice and fine-tuning the PN composition.

#### Arm B: Standard Parenteral Nutrition using 2/3-chamber bags

-CONFIDENTIAL- Page 26 of 33

Patients randomized to Arm B will receive standard PN using 2/3-chamber bags (various manufactures) according to the routine used by the participating site.

The following displays a guidance for the PN composition administered in Arm B. The amounts listed are understood as daily dose. Underlying medical conditions, intolerance etc. must always be considered per individual patient.

#### Macronutrients:

For the macronutrients, body weight is understood as the ideal body weight for the patient according to a BMI of 19 - 24 for women and 20 - 25 for men.

Glucose:  $\geq 2.0 - 4.0$  g per kg body weight Amino acids: 1.2 - 1.5 g per kg body weight Lipids: 0.5 - 2.0 g per kg body weight

#### Micronutrients:

Independent of the ideal body weight, should be added taken the actual serum levels into account.

Sodium: 60 - 150 mmolPotassium: 40 - 100 mmolMagnesium: 4 - 12 mmolCalcium: 2.5 - 7.5 mmol

Phosphate: 10 - 30 mmol

#### **Trace Elements and Vitamins:**

Trace Elements and Vitamins are added according to the standard dietary reference intake.

#### Water:

The amount of water depends on the oral intake of water, volume tolerance and kidney function. As general guidance 30 - 40 ml per kg body weight should be considered.

#### TOTAL:

Total Volume: 30 - 40 ml per kg body weight Total Calories: 25 - 30 kcal per kg body weight

guidance for calculating calories:

1 g glucose ~ 4 kcal

-CONFIDENTIAL- Page 27 of 33

1 g amino acids ~ 4 kcal 1 g lipids ~ 10 kcal

The investigator should specify the PN composition according to the site-specific routine in consultation with a nutritional expert, if routinely involved in the PN at this site, considering the guidance above. The investigator is free to use any manufacturer of traditional 2/3-chamber bags but should follow the site-specific routine. At the investigator's discretion he/she can also consult the Care Management/Supply Management of the respective manufacturer or of LIGETIS. Examples of manufactures providing 2/3-chamber bags are Braun (Nutriflex portfolio), Fresenius (SMOF Kabiven or Kabiven portfolio) or Baxter (Olimel portfolio).

-CONFIDENTIAL- Page 28 of 33

#### 9 Treatment schedule and schedule of assessments

The treatment schedule is displayed in Figure 4.

[figure not shown]

Figure 2: Treatment schedule and schedule of assessments.

\* The indication for PN will usually come from a physician during routine treatment in a hospital inpatient or outpatient setting and should be given independent of the trial.. The patient might have started PN already during routine (inpatient) treatment. PN=Parenteral nutrition (here: potential run-in phase); ET-G= standard low glucose HPN in Eurotubes®; ET= standard HPN in Eurotubes®; 2/3=standard HPN in 2/3-chamber bags; HPN=Home Parenteral nutrition in any PN bag; w=week; m=month, yr=year.

Please note: the protocol visits may be less frequent than the medically indicated visits. Please schedule visits as it is usual in your study site independent of the study but at least as frequent as indicated in this protocol. Reportable events occurring in other visits (scheduled or unscheduled) other than those required here should be reported in the eCRF with the documentation of the subsequent protocol visits.

-CONFIDENTIAL-

#### 9.1 Schedule of assessments

The schedule of assessments is displayed in Table 1. The assessments are the same irrespective of the treatment arm.

**Table 1: Schedule of Assessments** 

Schedule of Assessments	Screening	Visit 1 – Visit 12¹	EOT Visit	Follow- Up 
Informed consent 	X			
ECOG	X 	X	$X^{16}$	
Modified Glasgow Prognostic Score (mGPS)	$X^4$	X	X	
Nutritional Risk Screening	X 			
Physical Examination	X	X	$X^{16}$	
Weight	X	X	$X^{16}$	
Height	X			
Medical History	X			
Demographics, other baseline parameters	X			
Concomitant anti-cancer therapy (if any)	X 	$X^6$	$X^6$	
Laboratory 	X	X	X	
Pregnancy test 	X			
Catheter Related Infections (CRI)	X	X	X	
Any catheter related complications	X	X	X	
Adverse Events 	X	X	X	(X)
Medical device deficiencies 		X	X	
QoL questionnaire 	X	X	$X^{16}$	
Patient's study diary	$X^{12}$	$X^{13}$	$X^{13}$	
HPN therapy plan / administration/documentation		X 	X 	
Post discontinuation PN				$X^{15}$
Overall survival		X	X	X

- (1) A maximum of 12 visits should be documented within the study. The visit schedule itself is up to the clinical routine at the site and may occur approx. every four weeks. However, only the first visit within each four-week interval (starting from randomization) will be documented. If there is more than one visit within a four-week interval, only the first visit will be documented.
- (2) Every 3 months (+/- 2 weeks) until death or end of the study for survival status.
- (3) Mandatory prior to any study procedure.
- Should be (re-)determined by the study personnel even if known through the documentation received by the inpatient facility. Please note: ECOG PS of 0, 1, 2 and 3 are eligible for the trial.
- (5) Any anti-cancer therapy (including surgery and radiation) should be documented.
- (6) Changes in the anti-cancer therapy should be documented
- (7) Routine peripheral blood lab usually done in patients receiving HPN including but not limited to: Complete blood count (German: kleines Blutbild), albumin, total protein level (German: Gesamteiweiß), CRP, GOT (AST), GPT (ALT), LDH, cholinesterase, creatinine, triglycerides, urea, glucose, electrolytes (sodium, potassium, magnesium, calcium, phosphate) should be

-CONFIDENTIAL- Page **30** of **33** 

- determined according to local lab routine. Laboratory assessments do not need to be repeated at screening if laboratory assessments were done prior to screening within clinical routine and results are not older than 2 weeks.
- (8) In case of women of child-bearing potential. Serum pregnancy test at Screening.
- (9) Adverse Events (related or not) are captured at any time throughout the study as soon as they become known to the study team, beginning after the patient has given written informed consent and up to 14 days after the last study treatment was administered.
- (10) Medical device deficiencies are captured from randomization until last study specific HPN.
- (11) The site staff instructs the patient of how to complete the QoL questionnaire. Questionnaire is completed during all documented study visit until EOT. Results of the completed QoL questionnaire(s) are transcribed to the eCRF by the site.
- The site staff instructs the patient how to complete the patient's study diary. Handing out of a diary covering enough days until the next planned visit. Patient should complete diary daily until EOT. Please note: patients' diary is very important as it includes information on one of the study primary endpoint!
- (13) Results of the completed study diary are transcribed to the eCRF. Handing out of new diaries as needed.
- (14) Adjustments of the PN therapy plan are possible throughout the study, independent from the planned study visits. The latest adjustment will be documented at the time of each visit. The PN is administered at home through the nursing service, a caregiver or the patient.
- (15) After EOT, subsequent HPN/PN will be captured (only manufacturer).
- (16) If results of examinations are available which are not older than 14 days no further examination will be necessary.

**Important note:** These assessments are required by the study protocol. All examinations are part of routine clinical practice. It is important to note that the study protocol does not limit the examinations to the points mentioned above. The investigator shall perform all other/additional routine or site-specific examinations relevant to the safety of the patient or for any other procedures done.

-CONFIDENTIAL- Page 31 of 33

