#### 5.2.2 Secondary endpoints

#### Efficacy endpoints

- Relative weight change determined at baseline and during study visits approx. every four weeks after enrolment;
- Relative change of albumin and CRP levels measured at baseline and during regular study visits;
- Overall survival (OS) defined as the time from randomization to death from any cause.

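### Documenting the first visit of any kind in each four-week interval makes time on PN at a given visit number depend on how often the patient attends, and lets an acute visit replace the regular one

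*Combined protocol and SAP*

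**What the plan says.** Section 4 provides for "one visit per four-week interval after randomization for a maximum of 12 months" and does not say where in the interval that visit should fall. Table 1, footnote 1 (section 9.1) does: "only the first visit within each four-week interval (starting from randomization) will be documented". It repeats the rule for patients seen more often: "If there is more than one visit within a four-week interval, only the first visit will be documented". It leaves timing to the site: "The visit schedule itself is up to the clinical routine at the site and may occur approx. every four weeks". Section 9 adds that "the protocol visits may be less frequent than the medically indicated visits".

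These visits supply several secondary endpoints. In section 5.2.2, weight is "Relative weight change determined at baseline and during study visits approx. every four weeks after enrolment", and albumin and CRP change are taken at regular study visits. Section 4 also places weight and laboratory tests at regular visits. Footnote 11 ties the QoL questionnaire to documented visits. Footnote 1 itself speaks only of a visit, without the word regular.

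Survival follow-up has a window of 2 weeks either side (footnote 2); Visits 1 to 12 have none. Section 6.3.2 compares continuous variables by t-test, mentions no adjustment for the day of measurement, and leaves further detail to a later SAP.

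**The concern.** Weight, CRP and albumin are analysed as change from baseline, so the time on PN at measurement matters, most of all at the early visits. Under footnote 1 that time is set by how often the patient happens to attend. A patient seen weekly has Visit 1 within the first week; a patient seen every four weeks may have it as late as day 28. Both values carry the same visit number and enter the same comparison.

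The second problem is which visit is chosen. Footnote 1 does not separate planned from unplanned visits. If a consultation for fever or a catheter problem is the first contact in an interval, its CRP, albumin, weight and QoL stand for that interval, and the later regular visit is not recorded. Analysis by actual date could later allow for unequal timing. It could not recover values that were never documented.

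**Working it through.** **Inputs.** From the protocol: four-week intervals counted from randomisation, first visit documented, at most 12 documented visits (12 x 28 = 336 days). The protocol states no timing figure that could be reproduced and no attendance frequency. Attendance every f = 7, 14, 21 or 28 days is therefore an assumption covering a plausible range.

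**Step 1: regular attendance counted from randomisation.** Take the first visit in each interval from day 28(k-1)+1 to day 28k.

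| Attendance | Documented days | Gaps (days) |
|---|---|---|
| every 7 days | 7, 35, 63, ... | 28 |
| every 14 days | 14, 42, 70, ... | 28 |
| every 21 days | 21, 42, 63, 105, ... | 21, 21, 42, repeating |
| every 28 days | 28, 56, 84, ... | 28 |

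At 3-weekly attendance the third interval contains days 63 and 84, and day 84 is discarded. Visit 1 reflects about one week of study PN in one patient and four weeks in another.

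**Step 2: starting day not aligned with randomisation.** If the first visit is equally likely on any of days 1 to f, the mean Visit 1 day is (f+1)/2 and its variance is (f^2-1)/12.

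| f | Mean day | Variance | SD |
|---|---|---|---|
| 7 | 4.0 | 48/12 = 4.00 | 2.0 |
| 14 | 7.5 | 195/12 = 16.25 | 4.0 |
| 21 | 11.0 | 440/12 = 36.67 | 6.1 |
| 28 | 14.5 | 783/12 = 65.25 | 8.1 |

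A simulation with a continuous random start gave a mean day within the interval of 3.5, 6.9, 10.5 and 14.3, in agreement apart from the half day due to whole-day counting.

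**Step 3: what a target-day rule would change.** Choosing the visit nearest day 28 centres every frequency at about day 28. The spread within each frequency stays the same, because the nearest visit still ranges over f consecutive days. Only the differences between the frequency means disappear.

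For an equal mix of the four frequencies (assumed):
- within-frequency variance: (4.00 + 16.25 + 36.67 + 65.25)/4 = 30.54
- variance of the means 4, 7.5, 11, 14.5 around 9.25: (27.56 + 3.06 + 3.06 + 27.56)/4 = 15.31
- printed rule: SD = sqrt(30.54 + 15.31) = 6.8 days
- target-day rule: SD = sqrt(30.54) = 5.5 days

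The gain depends on the mix. If all patients attend at one frequency, it is nil. If half attend weekly and half 4-weekly, the within variance is (4.00 + 65.25)/2 = 34.63 and the variance of the means is ((14.5 - 4)/2)^2 = 27.56. The SD then falls from sqrt(62.19) = 7.9 to sqrt(34.63) = 5.9 days.

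**Step 4: acute visits.** No arithmetic applies. Sections 4 and 5.2.2 say regular visits; footnote 1 says any first visit. Section 9 covers events at other visits, scheduled or unscheduled, which are reported with the subsequent protocol visit. It does not say that an unscheduled visit cannot itself be the documented one.

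**The case against.** Several points against the concern stand.

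- A reader might infer that values are taken two to three weeks too early. The protocol does not support that. It names no day 28k, only a spacing of about four weeks, and the printed rule delivers this: gaps average 28 days. A patient seen on days 28, 56 and so on has no lag.
- A reader might also infer bias between arms. Section 3.5 expects fewer complications with Eurotubes, so acute visits could be selected more often in Arm B, and CRP and albumin would then partly repeat the infection endpoint. That requires attendance to differ by arm, and nothing in the documents shows that it does. Concurrent systemic anti-cancer treatment, the obvious reason for frequent attendance, is a stratification factor in both randomisations (section 4).
- The word regular in sections 4 and 5.2.2 supports reading acute visits as excluded. That is a reasonable reading, but footnote 1, which a site will follow, does not carry it.
- The primary endpoint comes from the daily diary. Adverse events are captured at any time (footnote 9), and secondary p-values are descriptive (section 6.3.2). The later SAP could use actual dates, but the protocol does not say that it will.
- The first visit is known on the day, whereas the closest visit may depend on what follows. This is largely met: sites already hand out diaries to last until the next planned visit (footnote 12), so the plan is known, and most patients who stop early have an EOT visit.

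**Conclusion.** The concern holds in a limited form. Under footnote 1 the time on PN at a given visit number depends on attendance frequency, with a mean Visit 1 day of about 4 to 14.5 across weekly to 4-weekly attendance. Read literally, the footnote also lets an acute visit take the place of the regular one. The consequence is noise and blurred visit numbers for weight, CRP, albumin and QoL, which are descriptive secondary endpoints. Bias between arms is possible only if attendance differs by arm. The figures rest on assumed frequencies and random starting days, and the SD reduction from 6.8 to 5.5 days also assumes an equal mix of frequencies. The change is worth making because it breaks the link between attendance and measurement day and stops acute visits from being selected, at little cost. It is not critical to the trial's main conclusion.

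**What to change.** Reword footnote 1 so that the documented visit is the regular (planned) visit closest to day 28 x k after randomisation, for k = 1 to 12, within 14 days either side. Adjacent windows meet at their edges, so say which k a visit exactly midway belongs to. Allow an unscheduled acute visit to serve only if no regular visit falls in the window. Keep the section 9 rule for reporting events from other visits, and keep the EOT visit for patients who stop early. State in the SAP that weight, CRP, albumin and QoL are analysed by actual days since randomisation.

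The cost is one footnote, the eCRF guide and a sentence in the SAP, with no extra visits or tests. There are two downsides. Sites must pick the visit from the planned schedule rather than at first contact. A patient who dies before the first window without an EOT visit contributes no early value, where the printed rule might have captured one.
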